3.3.4 Withdrawal of patients from treatment or assessments

Patients may discontinue trial treatment or withdraw consent to trial participation as a whole ("withdrawal of consent") with very different implications; please see Sections [3.3.4.1](#) and [3.3.4.2](#) below.

Measures to control the withdrawal rate include careful patient selection, appropriate explanation of the trial requirements and procedures prior to trial enrolment, as well as the explanation of the consequences of withdrawal.

The decision to discontinue trial treatment or withdraw consent to trial participation and the reason must be documented in the patient files and eCRF. If the reason for discontinuation is death, this should be reported on the SAE form as well, regardless of causal relationship.

3.3.4.1 Discontinuation of trial treatment

An individual patient will discontinue trial treatment if:

- The patient wants to discontinue trial treatment, without the need to justify the decision.
- The patient experiences signs of hepatic injury, defined in Section [5.2.10.1.4](#).
- In the opinion of the investigator, the patient experiences unacceptable adverse events despite dose adjustments and supportive care.
- The patient has repeatedly shown to be non-compliant with important trial procedures and, in the opinion of both, the investigator and sponsor representative, is not willing or able to adhere to the trial requirements in the future.
- Pregnancy (refer to Section [5.2.10.2.4](#)).
- The patient needs to take concomitant medication that interferes with the investigational medicinal product or other trial treatment. See also Section [4.2.2](#) for restricted or not-allowed medication.
- The patient can no longer receive trial treatment for medical reasons (such as surgery, adverse events, or other diseases).

In case of a temporary reason, trial treatment should be restarted if medically justified, please see Section [4.1.4](#).

3.3.4.2 Recommendation to discontinue nintedanib

In the following cases discontinuation of nintedanib is highly recommended. Only in special circumstances, the Investigator, upon thorough assessment of all available clinical data and taking into consideration the potential risks associated with administration of nintedanib, may decide not to withdraw the trial medication, even though one or more of the below mentioned criteria are fulfilled. In such a case, continuation of treatment with trial medication should be discussed with the patient, and the decision and reasoning documented in the source data.

- Major surgery, including any abdominal or intestinal surgery.
- Anti-coagulation. Patients who require full-dose therapeutic anticoagulation (e.g. vitamin K antagonists, heparin, hirudin, direct thrombin inhibitors, etc), or high-dose antiplatelet therapy. (Prophylactic low dose heparin or heparin flush as needed for maintenance of an indwelling intravenous device (e.g. enoxaparin 4000 IU s.c. per day), as well as

prophylactic use of antiplatelet therapy (e.g. acetyl salicylic acid up to 325 mg/day, or clopidogrel at 75 mg/day, or equivalent doses of other antiplatelet therapy is allowed.).

- Major thrombo-embolic events e.g. stroke, deep vein thrombosis, pulmonary embolism, myocardial infarction during the trial.
- Confirmed severe hypertension, uncontrolled under treatment ($\geq 160/100$ mmHg) during the trial
- Unstable cardiac angina during the trial
- Increased risk of bleeding e.g. hemorrhagic CNS event, gross / frank haemoptysis or haematuria, active gastro-intestinal bleeding or GI-ulcers during the trial.
- Scleroderma renal crisis during the trial
- Significant pulmonary hypertension during the trial, defined by any of the following:
 - New clinical or echocardiographic evidence of significant right heart failure
 - Right heart catheterisation showing a cardiac index ≤ 2 l/min/m²
 - PH requiring therapy prostacyclines (parenteral or oral, e.g. epoprostenol, treprostinil, selexipag)

Given the patient's agreement, the patient will undergo the procedures for early treatment discontinuation and follow up as outlined in the [Flow Chart](#) and Section [6.2.3](#).

For all patients, the reason for withdrawal (e.g. adverse events) must be recorded in the electronic Case Report Form (eCRF). These data will be included in the trial database and reported.

If one of the following situations occurs, the patient may be replaced after discussion between investigator and the Clinical Trial Leader (CT Leader), former Trial Clinical Monitor (TCM)).

- Microgynon[®] cannot be administered in Period 1 and Period 2
- Interruption of nintedanib therapy for more than 8 weeks.
- No continuous intake of 10 consecutive days possible within this trial
- Dose reduction of nintedanib to less than 2 x 100 mg per day before end of PK sampling
- Administration of forbidden drugs (refer to Section [4.2.2.1](#))
- Noncompliance with dietary restrictions, or parenteral feeding requirement
- Inability of the patient to comply with the food intake on the days of Microgynon[®] administration

3.3.4.3 Withdrawal of consent to trial participation

Patients may withdraw their consent to trial participation at any time without the need to justify the decision.

If a patient wants to withdraw consent, the investigator should be involved in the discussion and explanation to the patient.

When the patient prematurely discontinues the trial medication a follow-up Visit will be done 7 days after last intake of nintedanib, please see Section [3.3.4.1](#) above and the [Flow Chart](#).

3.3.4.4 Discontinuation of the trial by the sponsor

Boehringer Ingelheim reserves the right to discontinue the trial overall or at a particular trial site at any time for the following reasons:

1. Failure to meet expected enrolment goals overall or at a particular trial site.
2. Emergence of any efficacy/safety information invalidating the earlier positive benefit-risk-assessment that could significantly affect the continuation of the trial.
3. Violation of GCP, the trial protocol, or the contract impairing the appropriate conduct of the trial.

The investigator / the trial site will be reimbursed for reasonable expenses incurred in case of trial termination (except in case of the third reason).

4. TREATMENTS

4.1 INVESTIGATIONAL TREATMENTS

All patients will be treated with Microgynon[®] and nintedanib. Both Microgynon[®] and nintedanib will be considered as Investigational Medicinal Product (IMP) in this trial.

4.1.1 Identity of the Investigational Medicinal Products

Table 4.1.1: 1 Microgynon[®]

Substance:	Combination of ethinylestradiol and levonorgestrel
Pharmaceutical formulation:	Tablet
Source:	
Unit strength:	30 microgram ethinylestradiol (EE) /150 microgram levonorgestrel (LE) per tablet
Posology:	1 tablet (in each trial period)
Route of administration:	Oral

Table 4.1.1: 2 Nintedanib soft gelatine capsule

Substance:	Nintedanib
Pharmaceutical formulation:	Soft gelatine capsule
Source:	Boehringer Ingelheim Pharma GmbH & Co. KG
Unit strength:	150 mg per capsule (or 100 mg per capsule, in case of dose reduction*)
Posology:	b.i.d.
Route of administration:	Oral

Note: *Nintedanib shall be taken continuously throughout Period 2. In case of a temporary interruption of nintedanib intake or a dose reduction, patients can receive Microgynon[®] in Period 2 only if they have taken a stable dose of nintedanib for at least 10 consecutive days before intake of Microgynon[®]

4.1.2 Selection of doses in the trial and dose modifications

Based on the efficacy, safety and dose-finding from trials investigating nintedanib in IPF, TOMORROW (P11-11216), INPULSIS I and INPULSIS II (P14-07514), a dose of 150 mg b.i.d. was selected. With 150 mg b.i.d., acceptable tolerability in Systemic Sclerosis patients is expected based on the risk profile seen in IPF patients. Lower starting doses may not be expected to demonstrate efficacy based on the dose ranging trial (TOMORROW) in IPF.

However, to manage adverse events, the dose may be reduced to 100 mg b.i.d. (refer to Section [4.2.1](#) and Section [6.2.2](#)).

Microgynon[®] will be administered as a single administration on the PK profiling days only. One tablet of Microgynon[®] will be administered on the first PK day in in Period 1 and one tablet of Microgynon[®] on the first PK day in Period 2.

4.1.3 Method of assigning patients to treatment groups

This is a fixed sequence trial. After assessment of all in- and exclusion criteria, each eligible patient will undergo the respective treatment periods in an identical order.

An Interactive Response Technology (IRT) will be used for this trial, which will manage the IMP shipments to and returns from the sites. Allocation of the trial medication to the patient will be done by the investigator or delegated person at the site. Further details will be provided in the ISF.

The site will receive a sufficient supply of uniquely numbered Microgynon[®] and nintedanib treatment packages and initially one Microgynon[®] blister package (containing 21 tablets) and two (150 mg) nintedanib boxes will be assigned per patient. Additional nintedanib bottles (containing 150 mg or 100 mg nintedanib capsules) will be assigned to a patient when needed, e.g. if a patient has an adverse event (AE) resulting in temporary nintedanib interruption or dose reduction leading to prolongation of the total treatment period. (See further details in Section [4.1.4](#)).

The assigned Microgynon[®] and nintedanib medication numbers will be recorded in the eCRF for that patient.

4.1.4 Drug assignment and administration of doses for each patient

Patients will take one tablet of Microgynon[®] at least 3 days before the first intake of nintedanib (at Visit 2 in Period 1) and one tablet of Microgynon[®] after continuous nintedanib administration for at least 10 consecutive days (at Visit 6 in Period 2). The remaining 19 tablets in the Microgynon[®] blister will not be used.

Nintedanib will be taken by the patients at home except for the PK profiling days. The patients will be handed out the nintedanib medication (two bottles with 30 capsules each, containing 150 mg nintedanib per capsule, for the respective time period) at the time point indicated in the [Flow Chart](#).

Nintedanib will be administered orally on a twice daily basis (b.i.d.). The nintedanib capsule should be taken with food, swallowed whole with water (~250 mL) and must not be chewed or crushed. Nintedanib needs to be taken with a dose interval of approximately 12 hours, i.e. at approximately the same time every day: one capsule between 06:00 and 11:00 in the morning, and one capsule between 18:00 and 23:00 in the evening.

Nintedanib treatment (150 mg twice daily) will start at Visit 5 (Day 1) and will continue at stable dose for at least 14 days, in order to ensure that at least 10 days of continuous nintedanib treatment is taken before the PK profiling in Period 2 will start at Visit 6. The patient will have the last intake of nintedanib trial medication the evening prior to, or at the

End of Treatment (EOT) Visit, which has to take place at least 3 days after Microgynon[®] intake at Visit 6.

On both PK profile days (the first PK days in Period 1 and Period 2), a standardised meal (breakfast) has to be consumed within 30 minutes prior to Microgynon[®] intake. A standardized meal means that, for the individual patient, the meal should preferably be identical in Period 1 and Period 2. 30 Minutes after start of the standardised meal, Microgynon[®] will be administered. On the day of Microgynon[®] administration in Period 2, the morning dose of nintedanib will be taken first, immediately followed by the Microgynon[®] tablet and both have to be taken within one minute.

The trial drugs will be administered in the standing position under supervision of the investigating physician or an authorized designee.

During the first 4 h after Microgynon[®] administration on the PK profile days, patients are not allowed to lie down (i.e. no declination of the upper body of more than 45 degrees from upright posture) unless supine positioning is required for trial related measurements.

The patient shall be instructed to not skip any doses. A forgotten or missed dose must be skipped if the time window to the next dose is less than 8 hours. The next dose should be taken as scheduled. Under no circumstances should two doses be taken at the same time. In case of vomiting, the patient should not take a replacement dose.

The investigational product should only be dispensed to participating patients according to the protocol by authorised personnel as documented in the form "Investigator's Trial Staff List". The authorized person(s) must instruct the patients on how and when to take the medication, how to store it and when to return the used and unused medication (bottles), in addition to the instructions on the label.

In case of adverse events requiring dose reduction between planned visits (see Section [4.2.1](#) for details) an additional site visit is required. The dose can be reduced without prior interruption, i.e., immediately stepping down from 150 mg b.i.d. to 100 mg b.i.d. The color of capsules (100 mg capsule) will be slightly different.

Patients experiencing adverse events requiring temporary interruption of trial medication may re-start trial medication according to procedures described in Section 4.2.1.

4.1.5 Blinding and procedures for unblinding

4.1.5.1 Blinding

Not applicable, since this is an open-label trial with only one fixed treatment sequence.

4.1.5.2 Unblinding and breaking the code

Not applicable.

4.1.6 Packaging, labelling, and re-supply

Nintedanib will be provided by Boehringer Ingelheim (BI) or a designated Contract Research Organisation (CRO) and will be packaged and labelled in accordance with the principles of Good Manufacturing Practice (GMP).

Depending on local laws and regulations in the countries of the participating sites, Microgynon[®] will be provided by BI or a designated CRO and packaged and labelled in accordance with the principles of Good Manufacturing Practice (GMP). For details of packaging and the description of the label, refer to the ISF.

An IRT system will be used to manage the shipment of open-label trial medication supplies to the site, and returns and destruction.

A re-supply of trial medication is not planned, but can be managed by the IRT system, if necessary, e.g. if the trial treatment expires due to unexpected prolongation of the study. In that case the medication for re-supply will be packaged in an identical manner as the medication for initial supply.

4.1.7 Storage conditions

Drug supplies will be kept in their original packaging and in a secure limited access storage area according to the recommended storage conditions on the medication label. A temperature log must be maintained for documentation.

If the storage conditions are found to be outside the specified range, the local clinical monitor (as provided in the list of contacts) must be contacted immediately.

4.1.8 Drug accountability

The investigator or designee will receive the investigational drugs delivered by the sponsor when the following requirements are fulfilled:

- Approval of the clinical trial protocol by the Institutional Review Board (IRB) / Independent Ethics Committee (IEC),
- Availability of a signed and dated clinical trial contract between the sponsor and the investigational site,
- Approval/notification of the regulatory authority, e.g. competent authority,
- Availability of the curriculum vitae of the Principal Investigator,
- Availability of a signed and dated clinical trial protocol,
- In countries where it is required, availability of the proof of a medical license for the Principal Investigator,

Investigational drugs are not allowed to be used outside the context of this protocol. They must not be forwarded to other investigators or clinics. Patients should be instructed to return unused investigational drug.

The investigator or designee must maintain records of the product's delivery to the trial site, the inventory at the site, the use by each patient, and the return to the sponsor or warehouse / drug distribution centre or alternative disposal of unused products. If applicable, the sponsor or warehouse / drug distribution centre will maintain records of the disposal.

These records will include dates, quantities, batch / serial numbers, expiry ('use-by') dates, and the unique code numbers assigned to the investigational medicinal product and trial patients. The investigator or designee will maintain records that document adequately that the patients were provided the doses specified by the Clinical Trial Protocol (CTP) and reconcile all investigational medicinal products received from the sponsor. At the time of return to the

sponsor and/or appointed CRO, the investigator or designee must verify that all unused or partially used drug supplies have been returned by the clinical trial patient and that no remaining supplies are in the investigator's possession.

4.2 OTHER TREATMENTS, EMERGENCY PROCEDURES, RESTRICTIONS

4.2.1 Other treatments and emergency procedures

Rescue medications to reverse the action of nintedanib are not available.

Dose reduction (from 150 mg b.i.d. to 100 mg b.i.d.) or treatment interruption should be considered to manage adverse events. No further dose reduction is possible for patients on the 100 mg b.i.d. regimen. In case of persistent adverse events observed at this dose, or severe effects at 150 mg b.i.d., requiring a second treatment interruption or interruption longer than 8 weeks, the nintedanib treatment must be permanently discontinued.

There are no specific rescue drugs foreseen for the treatment of AEs. No special emergency procedures are to be followed.

Table 4.2.1: 1 Allowed treatment reduction / interruption periods:

	AEs considered drug related	AEs not considered drug related
Number of interruptions	One	One
Maximum interruption	4 weeks	8 weeks
Recommended restart	with reduced dose (100 mg b.i.d.).	with the same dose (150 mg b.i.d), or reduced dose (100 mg b.i.d.)

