4.2.1.1 Management of diarrhoea

Other causes for diarrhoea should always be considered and treated accordingly (e.g. viral infections, SSc related diarrhoea, bacterial overgrowth, antibiotic treatment).

Diarrhoea should be managed as early as possible after onset of first symptoms with standard anti-diarrhoeal symptomatic treatment, e.g. loperamide.

If diarrhoea persists despite optimal symptomatic treatment, treatment interruption and dose reduction of nintedanib should be considered based on the recommendations described in Table [4.2.1.1: 1](#).

If a patient is having diarrhoea prior to, or during the PK profiling in Period 1 or Period 2 then the PK profiling should be postponed, since this may affect the efficacy of both medicines Microgynon[®] and nintedanib and therefore also the PK.

Table 4.2.1.1: 1 Management of diarrhoea (considered related to nintedanib)

Description	Symptomatic Treatment ¹	Action with nintedanib
Diarrhoea with increase of <4 stools per day over baseline ² .	Initiate anti-diarrhoeal medicines at first signs of symptoms (e.g. 4 mg loperamide followed by 2 mg after each loose stool or every 2-4 hours to a maximum of 16 mg/day) until bowel movements cease for 12 hours.	Continue same nintedanib dose.
Diarrhoea with increase of 4 to 6 stools per day over baseline ² .	Initiate/continue anti-diarrhoeal medicines; If diarrhoea of this severity persists for ≥48 to 72 hours assess for dehydration and electrolyte imbalance; In addition, consider intravenous (IV) fluids and electrolyte replacement as clinically indicated.	If diarrhoea persists for ≥48 to 72 hours despite optimal symptomatic care: 1. Interrupt nintedanib until recovery ³ . 2. Reduce dose to 100 mg b.i.d. after recovery.
Diarrhoea with increase of ≥7 stools per day over baseline ² ; stool incontinence, or life threatening consequences.	Follow recommendations above. In addition, consider stool work-up to exclude infectious colitis; adequate IV fluid replacement ≥24 hours, hospitalisation as clinically indicated; consider referral to a GI specialist to rule out potential differential diagnoses.	1. Interrupt nintedanib until recovery ³ . 2. Reduce dose to 100 mg b.i.d. after recovery. In case of reoccurrence of diarrhoea of this severity despite optimal symptomatic treatment and dose reduction, treatment with nintedanib should be permanently discontinued.

Footnotes:

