¹ Other causes for diarrhoea should always be considered and treated accordingly (e.g. viral infections, SSc related diarrhoea, bacterial overgrowth, antibiotic treatment). The use of loperamide should be avoided 72 hours prior to and during PK sampling days (see Table 4.2.2.1: 1), so in case his happens it is advised to postpone or interrupt the PK assessments and to repeat the PK assessments again after 10 days of nintedanib use, if possible and agreed by patient and investigator.

² Baseline defined as usual stools/day prior to start of nintedanib at Day 1 (Visit 5) of Period 2.

³ See Section 4.2.1: Maximum interruption of 4 weeks allowed, if diarrhoea is related to nintedanib. If diarrhoea is not recovered within 4 weeks, the patient must be discontinued from treatment and the trial.

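### Protocol Section 4.2.1 gives no single stopping rule after nintedanib interruptions: the count conflicts between text and tables, and the action for other drug-related interruptions of more than 4 and up to 8 weeks is inconsistent

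*Protocol*

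**What the plan says.** Four places in the protocol bear on how often, and for how long, nintedanib may be interrupted.

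- **Section 4.2.1, text.** For adverse events persisting at 100 mg b.i.d., or severe effects at 150 mg b.i.d.: "requiring a second treatment interruption or interruption longer than 8 weeks, the nintedanib treatment must be permanently discontinued". Neither the count nor the 8 weeks depends on cause.
- **Section 4.2.1, Table 4.2.1: 1**, titled "Allowed treatment reduction / interruption periods". It has one column for drug-related events and one for events not considered drug related. The rows read "Number of interruptions One One" and "Maximum interruption 4 weeks 8 weeks". After an unrelated event, restart at 150 mg b.i.d. is among the options.
- **Section 4.2.1.1, Table 4.2.1.1: 1 and footnote 3 (diarrhoea).** In the most severe category, nintedanib is interrupted and restarted at the reduced dose after recovery. The stop comes later: "In case of reoccurrence of diarrhoea of this severity despite optimal symptomatic treatment and dose reduction, treatment with nintedanib should be permanently discontinued". Footnote 3 refers back to Section 4.2.1: "Maximum interruption of 4 weeks allowed, if diarrhoea is related to nintedanib". It adds: "If diarrhoea is not recovered within 4 weeks, the patient must be discontinued from treatment and the trial".
- **Section 3.3.4.2, replacement list.** One situation in which a patient may be replaced is "Interruption of nintedanib therapy for more than 8 weeks", whatever the cause.

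Section 4.1.4 sends sites to Section 4.2.1 for restarting after an interruption. The Flow Chart notes and Section 3.1 allow Visit 6 to be postponed and its window extended, so a restarted patient can still have her Period 2 profile after 10 consecutive days on a stable dose.

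**The concern.** A site deciding whether a patient may go back on nintedanib is directed to a section whose text and table can give different answers. One site could stop her permanently on the text; another could restart her on the table, complete the 10 days and take the Period 2 profile. That is first a patient-safety matter, because exposure after a severe or drug-related event would depend on which lines a site applied.

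It also touches the data. Site interpretation could help decide who supplies a Period 2 profile, and SAP Table 6.2: 1 has no deviation code specific to exceeding an interruption limit. SAP Section 7.3 notes that compliance can be low after an interruption in a patient who still followed the protocol, so the compliance listing would not by itself identify such a case.

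**Working it through.** The plan gives no figure for this point, so the check is a comparison of rules. The Section 4.2.1 text and Table 4.2.1: 1 were each written as a decision rule and applied to eight patterns of cause, duration and number.

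- Text rule: stop if this is a second interruption or if it exceeds 8 weeks; otherwise no stop is mandated.
- Table rule: not allowed if there is more than one interruption in the same cause column, or if it lasts more than 4 weeks (related) or 8 weeks (unrelated); otherwise allowed.

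The patient is assumed to fall within the text's trigger (persistent at 100 mg b.i.d. or severe at 150 mg b.i.d.).

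| Pattern | Text | Table 4.2.1: 1 | Agree? |
|---|---|---|---|
| Related, 3 weeks | no stop mandated | allowed | yes |
| Related, 6 weeks | no stop mandated | not allowed | **no** |
| Related, 9 weeks | stop | not allowed | yes |
| Unrelated, 6 weeks | no stop mandated | allowed | yes |
| Unrelated, 9 weeks | stop | not allowed | yes |
| Unrelated 2 weeks, then related 2 weeks | stop | allowed | **no** |
| Two related, 2 weeks each | stop | not allowed | yes |
| Two unrelated, 2 weeks each | stop | not allowed | yes |

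**Count.** Take a patient with an unrelated interruption who restarts at 150 mg b.i.d., as the table permits. She then has a first episode of the most severe diarrhoea category, judged related to nintedanib.

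1. Text: this is a severe effect at 150 mg b.i.d. requiring a second interruption, so stop permanently.
2. Table 4.2.1: 1: this is the first interruption in the drug-related column, so it is allowed, with restart at the reduced dose.
3. Table 4.2.1.1: 1: interrupt, reduce after recovery, and stop only on recurrence.

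Step 1 cannot be followed together with steps 2 and 3.

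**Duration.** The band in question is more than 4 and up to 8 weeks (8 − 4 = 4 weeks wide), for drug-related events.

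1. Table 4.2.1: 1: the 4-week maximum is exceeded, with no consequence stated.
2. Text: the mandatory stop is not reached until 8 weeks are exceeded.
3. Replacement bullet: likewise not reached until 8 weeks are exceeded.
4. Diarrhoea related to nintedanib: footnote 3 closes the gap with a mandatory stop at 4 weeks.
5. Liver enzymes: Table 4.2.1.2: 1 and its footnote 5 have their own rule, with a permanent stop if values are still at or above 3 times the upper limit of normal after 2 weeks.

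The gap therefore remains for drug-related events other than diarrhoea and liver enzyme elevation.

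**Effect on the statistics.** Table 7.7: 1 (Section 7.7) reproduces at a gCV of 20% as exp[t(0.95, n−1) × √ln(1.04) × √(2/n) × √(χ²(0.95, n−1)/(n−1))]. This gives 1.190 for n = 14 and 1.214 for n = 12, as stated in the protocol. The interruption rules do not enter the formula; they can only affect how many patients reach the second profile. One patient is 1/14 = 7.1% of the planned evaluable set.

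**The case against.** The strongest reply is that the passages can be read together. The 4 and 8 weeks in Table 4.2.1: 1 belong to different causes and do not compete. The text's 8 weeks can be taken as an outer cap: it nowhere says that a drug-related interruption of 4 to 8 weeks may be restarted. A site restarting at 6 weeks after a drug-related event has exceeded the table maximum and is not following the protocol exactly. Footnote 3, which cites Section 4.2.1 for its 4 weeks, supports this reading. This largely stands. A reader might infer that the protocol contradicts itself outright on 4 versus 8 weeks; the documents do not support that. What survives is that, outside diarrhoea and liver enzymes, the table gives a maximum without a consequence while the general mandatory stop uses a later one.

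On the count, one could say that the second interruption in the text means a second one in the same cause column. That would remove the conflict, but the text does not say so.

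Two further inferences also go too far.

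- **That every patient with one related and one unrelated interruption gets opposite instructions.** The text covers only events persisting at 100 mg b.i.d. or severe at 150 mg b.i.d.; other second interruptions fall outside it.
- **That a patient stopped at 4 weeks could not be replaced.** She misses the 8-week bullet, but Section 3.3.4.2 lists other routes, including inability to complete 10 consecutive days. Replacement is discretionary, and Section 7.7 allows extra enrolment if fewer than 14 are evaluable.

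Finally, Visit 6 is normally due between Day 11 and Day 25, so these patterns need a disrupted course, and Section 3.3.4.1 already stops patients whose events the investigator finds unacceptable despite dose adjustment. Both points limit the frequency; neither settles which instruction applies.

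**Conclusion.** The point holds in a limited form. The count is a genuine conflict: for an unrelated interruption followed by a first most-severe nintedanib-related diarrhoea episode, the text requires a permanent stop and the two tables provide for a restart. This assumes that the severe category of Table 4.2.1.1: 1 is a severe effect in the sense of the text, which the protocol does not define, and that each column's single interruption is counted separately. The duration issue is weaker: an inconsistent trigger and a missing consequence, confined to drug-related events other than diarrhoea and liver enzyme elevation.

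The documents give no frequency for these patterns. The number affected is unknown and probably small, so the 7.1% is a weight per patient, not an expected loss. The sample-size and precision figures stand. The reason to act is that a mandatory stopping rule should not leave sites to choose between readings.

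**What to change.** Reconcile four places: the Section 4.2.1 text; Table 4.2.1: 1; Table 4.2.1.1: 1 with footnote 3; and the 8-week replacement bullet in Section 3.3.4.2. Together they should state:

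1. whether the permitted number of interruptions is counted per cause or in total;
2. one duration limit for each cause, the same wherever it appears;
3. what happens when a limit is exceeded, for all drug-related events and not only diarrhoea and liver enzymes.

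The replacement bullet should refer to the same limits. Which limits and which count apply is for the sponsor to decide. The cost is protocol wording in four places, with no new procedures, visits or patients, and no change to the planned analysis.
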